2.6 Interim Core Team Reviews

The core team will meet regularly to review safety data. Details can be found in the A5372 SPDSMP.

In addition, when DTG PK data from the first 32 evaluable participants in Arm 1 are available, an interim analysis of Arm 1 DTG PK data will be conducted by protocol pharmacologist and reviewed by the core team. The main purpose of this review is to determine whether Arm 2 should open, or the study should proceed with Arm 1 only. This analysis is described in Section 4.5 herein.

There will not be a formal SMC review to evaluate the interim DTG PK data; however, the SMC will be notified of the decision as soon as the PK interim review by the core team is completed.

3 Outcome measures

3.1 Primary Outcome Measures

The primary outcome measures are participant-specific estimates of the day 0 and day 28 plasma DTG PK parameters C_{max} , C_{min} , and area under the concentration-time curve over 24 hours (AUC_{0-24h}) while on the Arm 1 regimen and, if Arm 2 opens, the Arm 2 regimen. [Outcome Measure 10.2.1.1].

3.2 Secondary Outcome Measures

The secondary outcome measures for addressing the study’s secondary objectives are listed in protocol Section 10.2.2 as:

1. Proportion of participants exhibiting each of the following events during administration of DTG with 1HP, by arm [Outcome Measure 10.2.2.1]
 - a. Grade 3 adverse event(s) (AE(s))
 - b. Grade 4 AE(s)
 - c. Grade 3 or 4 AE(s)
 - d. AEs of grade 2 or higher
 - e. AEs that led to a change in study treatment regardless of grade
 - f. AEs meeting the serious adverse events (SAE) definition or EAE reporting requirements.
2. Proportion of participants who discontinue study or study drugs during DTG and 1HP dosing, by arm [Outcome Measure 10.2.2.2]. This includes discontinuation of DTG, RPT, INH, and NRTIs.
3. Proportion of participants with HIV-1 RNA levels >50 copies/mL at day 28 (-2/+14 days) and/or at the Follow Up visit [Outcome Measure 10.2.2.3].

4 Statistical considerations

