1.3 Secondary Objectives

- 1.3.1 To evaluate the safety of coadministration of DTG based ART with 1HP.
- 1.3.2 To evaluate the tolerability of coadministration of DTG based ART with 1HP.
- 1.3.3 To estimate the proportion of participants who maintain virologic suppression when DTG based ART is coadministered with 1HP.

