6.3.8 Virologic Studies

Plasma HIV-1 Viral Load

Obtain HIV-1 viral load per the SOE at a laboratory that possesses a CLIA certification or equivalent (US sites) or VQA certification (non-US sites).

Screening HIV-1 RNA must be performed within 30 days prior to study entry. Eligibility will be determined based on the screening value.

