10.2.2 Secondary Outcome Measures

- 10.2.2.1 Proportion of participants with all adverse events meeting the reporting criteria in [Section 7.2](#) during administration of DTG with 1HP, by arm.
- 10.2.2.2 Proportion of participants who discontinue study or study drugs during DTG and 1HP dosing, by arm.
- 10.2.2.3 Proportion of participants with HIV-1 RNA levels >50 copies/mL at Day 28 (-2/+14 days) and/or at the Follow Up visit.

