2.3.2 Secondary Objectives

1. To evaluate the safety of coadministration of DTG-based ART with 1HP [Objective 1.3.1].
2. To evaluate the tolerability of coadministration DTG-based ART with 1HP [Objective 1.3.2].

3. To estimate the proportion of participants who maintain virologic suppression when DTG-based ART is coadministered with 1HP [Objective 1.3.3].

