
IE: Failure to take DTG as prescribed (1) for 3 days prior to starting 1HP (Principal Stratum strategy)
 
IE: Failure to take DTG (1) and 1HP (2) as prescribed prior to steady state (Principal Stratum strategy)
 
(1) 6 BID 50 mg doses (Arm 1) or 3 QD 50 mg doses (Arm 2)
 
(2) 3 QD doses of 300 INH mg and 3 doses of 600 mg QD doses of RPT
 
For both intercurrent events the Principal Stratum is defined as having taken DTG and 1HP treatment as prescribed
	
Missing data may occur because of:
 
 Failure to appear at study visit (Day 0 or Day 28) Incomplete sampling (≥ 6 timepoints including both 23- and 24-hour samples) Incomplete/unevaluable concentrations when sampled (≥ 6 timepoints including both 23- and 24-hour samples) 
Missing samples and PK concentrations for participants otherwise meeting the dosing criteria will be assumed missing completely at random and participants excluded from the analysis.

Population-level summary measure	Analysis approach
Geometric mean ratio of DTG Cmax, Cmin, and AUC _{0-24h} with (after initiating 1HP; numerator) and without (prior to initiating 1HP; denominator) 1HP	Geometric mean ratio with associated 90% CIs. See Section 8 for details.

Sensitivity Analyses

No sensitivity analyses are planned.

Supplementary analyses

No supplementary analyses are planned.

4.9 Analysis Addressing the Safety, Tolerability and Virologic Suppression Secondary Objectives (Conducted by Statisticians)

For the Safety Analysis Population (see Section 4.2.3), proportions of the events listed in **Section 3.2** will be reported by arm: (a) the proportion of participants with Grade 3 or 4 AE during administration of DTG with 1HP; (b) the proportion of participants who discontinue study or study drugs during administration of DTG with 1HP; and (c) the proportion of participants with HIV-1 RNA levels >50 copies/mL at the second intensive PK measure and/or at the Follow Up visit. Proportions will be reported along with 95% exact Clopper-Pearson CIs around the proportions.

5 Report components

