5.3 Baseline Characteristics

The following characteristics (day 0) will be summarized by arm

- Summary of age, sex, race, and ethnicity.
- Summary of body weight and body mass index (BMI).
- Summary of plasma HIV-1 RNA (number below lower limit of quantification and, for participants with detectable viral load, statistical summary of \log_{10} copies); ARV regimen.

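### The virologic outcome takes no account of the Day 0 viral load, so viremia that began before 1HP and persists is counted against maintenance of suppression on 1HP

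*SAP*

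**What the plan says.** - **Objective.** Protocol 1.3 and SAP 2.3.2 share the aim. In the SAP's words: "To estimate the proportion of participants who maintain virologic suppression when DTG-based ART is coadministered with 1HP".
- **Outcome.** Protocol 10.2.2.3 defines it as "Proportion of participants with HIV-1 RNA levels >50 copies/mL at Day 28 (-2/+14 days) and/or at the Follow Up visit". SAP 3.2 item 3 repeats this: "Proportion of participants with HIV-1 RNA levels >50 copies/mL at day 28 (-2/+14 days) and/or at the Follow Up visit".
- **Analysis.** SAP 4.9 reports, by arm, "the proportion of participants with HIV-1 RNA levels >50 copies/mL at the second intensive PK measure and/or at the Follow Up visit", and adds: "Proportions will be reported along with 95% exact Clopper-Pearson CIs around the proportions". SAP 5.9 lists the same result.
- **Denominator.** The Safety Analysis Population (SAP 4.2.3) is defined only by doses of rifapentine, isoniazid and dolutegravir taken. It carries no viral load condition.
- **Entry.** Protocol 4.1.5 requires HIV-1 RNA below 50 copies/mL on a sample from the 30 days before entry. Protocol 6.3.8 adds: "Eligibility will be determined based on the screening value".
- **Day 0 value.** SAP 5.3 places plasma HIV-1 RNA among the Day 0 characteristics. It plans a count below the limit of quantification and, "for participants with detectable viral load, statistical summary of" log10 copies. No section connects this summary to the virologic outcome.

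**The concern.** A participant can maintain suppression on 1HP only if suppressed when 1HP starts. The outcome does not check this, the denominator does not impose it, and the entry criterion guarantees it only at a point up to 30 days earlier. A Day 0 value above 50 does not bar entry. If that viremia lasts to Day 28 or Follow Up, it enters the numerator as a failure on 1HP.

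There is no arm without 1HP, so nothing else in the trial shows how often values above 50 occur without the interaction. The pharmacokinetic comparisons use Day 0 as each participant's own reference (Protocol 10.1, SAP 4.7), but the virologic outcome, which is the clinical side of the same question, has no reference. Few events can be expected in a suppressed population of this size, so one or two misattributed cases could be the whole result. Protocol 10.5.1 also has the proportion above 50 reported at the Arm 1 interim review, so such cases would be in view there.

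**Working it through.** The documents state no expected rate, power or sample size for this outcome, so there is no figure of theirs to reproduce. The check has two parts.

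**1. How each pattern is classified.** Under SAP 3.2 and 4.9 only the two later visits matter.

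| Day 0 | Day 28 and Follow Up | Counted as >50? | Viremia began before 1HP? |
|---|---|---|---|
| ≤50 | ≤50 at both | No | – |
| ≤50 | >50 at either | Yes | No, on the Day 0 value |
| >50 | ≤50 at both | No | Yes, but resolved |
| >50 | >50 at either | Yes | Yes |

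The fourth row is the problem: it is pooled with the second.

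**2. Possible size.**

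Inputs:
- n = 36 per arm, the planned enrolment (Protocol 10.4, SAP 2.4). The Safety Analysis Population may differ somewhat from this.
- Exact 95% Clopper-Pearson interval (SAP 4.9).
- b = number above 50 at Day 0 and again at Day 28 or Follow Up. The documents do not give it; b = 1 to 3 is assumed.
- No new viremia on 1HP (assumed for the illustration).

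For x events in n, the lower limit is the 0.025 quantile of Beta(x, n − x + 1) and the upper limit is the 0.975 quantile of Beta(x + 1, n − x). For x = 0 the lower limit is 0 and the upper limit is 1 − 0.025^(1/n); for example, 1 − 0.025^(1/35) = 10.0%.

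| b | As planned | Restricted to Day 0 ≤50 |
|---|---|---|
| 0 | 0/36 = 0% (0 to 9.7%) | the same |
| 1 | 1/36 = 2.8% (0.1 to 14.5%) | 0/35 = 0% (0 to 10.0%) |
| 2 | 2/36 = 5.6% (0.7 to 18.7%) | 0/34 = 0% (0 to 10.3%) |
| 3 | 3/36 = 8.3% (1.8 to 22.5%) | 0/33 = 0% (0 to 10.6%) |

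Each persistent case adds 1/36 = 2.8 percentage points.

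How likely such cases are depends on a rate p of Day 0 values above 50, which is also assumed. The chance of at least one participant above 50 at Day 0 in an arm of 36 is 1 − (1 − p)^36. If half of those are still above 50 later (assumed), the expected number of misattributed events is 36 × p × 0.5.

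| Assumed p | Chance of at least one at Day 0 | Expected misattributed events |
|---|---|---|
| 1% | 30% | 0.18 |
| 5% | 84% | 0.9 |
| 10% | 98% | 1.8 |

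**The case against.** The strongest defence is that suppression at baseline is already required. Entry needs RNA below 50 within 30 days, at least 28 days of dolutegravir and NRTI dosing, and no self-reported gap of more than 3 consecutive days in the last 28 (Protocol 4.1.5, 4.1.7). A value above 50 after documented suppression is a reasonable reading of failure to maintain it. Any misattribution raises the failure count, which is the cautious direction for a safety outcome. No test or threshold rests on the outcome, and Arm 2 opens on pharmacokinetic criteria (Protocol 7.4, SAP 4.5). All of this stands. It limits how many participants are affected and what depends on them, but it does not separate viremia that began before 1HP from viremia that began on it.

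A reader might infer more than the documents support:

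- *That everyone above 50 at Day 0 counts as a failure.* They do not; the value must be above 50 again at Day 28 or Follow Up.
- *That SAP 5.3 expects participants above 50 at Day 0.* It provides for detectable values. Detectable does not mean above 50, and no assay limit is given.
- *That Day 0 is ignored altogether, or that every other analysis is within-person.* Day 0 RNA is summarised at baseline, and the within-person comparison is for the pharmacokinetic parameters. Adverse events and discontinuations are also plain proportions by arm.
- *That the outcome should be replaced.* It is listed in the protocol and destined for registry reporting (Protocol 10.2, SAP 1.1). Changing it in the SAP alone would make the two documents disagree.

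One uncertainty remains. The viral load row of the schedule of evaluations (Protocol 6.1) was not in the text available to me, and Protocol 10.5.1 names only Days 28, 42 and 49 for viral load monitoring. That a Day 0 sample exists is inferred from SAP 5.3; the wording of Protocol 6.3.8, which names the screening value as the one that decides eligibility, is compatible with it.

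**Conclusion.** The point holds in a limited form. The objective presupposes suppression at the start of 1HP, and neither the outcome, its denominator nor its analysis uses the Day 0 value. Viremia that was present before the first 1HP dose and persists is therefore counted against 1HP, in a trial with no arm without 1HP.

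The size is unknown, because the documents give no rate of Day 0 viremia. On the illustrative assumptions of 36 participants and no new viremia, one or two such cases would lift the exact 95% upper limit to 14.5% or 18.7%, against 10.0% or 10.3% in the restricted set. If nobody is above 50 at Day 0, the two analyses coincide. No sample size, power statement or Arm 2 criterion changes. This is a cheap improvement in interpretability, and the protocol-listed outcome can stand.

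**What to change.** Keep the outcome in Protocol 10.2.2.3 and SAP 3.2 item 3 as defined. In SAP 4.9 and 5.9 add, by arm:

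- (a) the same proportion, with its exact 95% Clopper-Pearson interval, among participants with Day 0 HIV-1 RNA at or below 50 copies/mL;
- (b) a cross-tabulation of Day 0 (above 50 or not) against Day 28/Follow Up (above 50 or not).

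Both use the Day 0 HIV-1 RNA that SAP 5.3 already summarises. Confirm against the schedule of evaluations that this value is a Day 0 sample and not the screening result carried forward; if it is the latter, the addition cannot be made as described. Specifying it in advance also avoids a later, data-driven decision to discount particular events.

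The cost is SAP wording, one extra table and a denominator for (a) that may be smaller by one or two. No new visit is needed if the Day 0 sample is confirmed.

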4.1 Times Used in the Primary and Secondary Outcome Measure Definitions

Day 0: The day of study enrollment and the first intensive PK sampling is conducted. At this point, participants have not taken any study provided medications.

Day 1: Start of study provided medications.

Day 3 (+2 days): First visit on study treatment. The first sparse PK sampling is conducted.

Day 14 (±2 days): Second visit on study treatment. The second sparse PK sampling is conducted.

Day 21 (±2 days): Third visit on study treatment. The third sparse PK sampling is conducted.

Day 28 (-2/+14 days): Last visit on study treatment. The second intensive PK sampling is conducted.

4.2 Analysis Populations

We define three analysis populations used for estimation of the estimands described in Section 4.8.

4.2.1 Primary PK Analysis Population

Primary PK Analysis Population (separately defined for Arm 1 and Arm 2 participants): The primary PK analysis population consists of those participants who: (1) met all study entry criteria, (2) initiated the 1HP TB regimen and completed 28 daily doses RPT/INH within the 6-week study period, and (3) took DTG twice-daily (Arm 1) or once-daily (Arm 2) for days 1-28 (that is, for the participant, both PK profiles are available (before initiating 1HP and while taking 1HP).

4.2.2 Secondary PK Analysis Population

Secondary PK Analysis Population (separately defined for Arm 1 and Arm 2 participants): The secondary PK analysis population consists of those participants who met all study entry criteria and for whom at least one DTG concentration is available where the dates, times and dose amounts of DTG doses in the three days leading up to the intensive PK sampling visit. Concentrations from all participants, not just evaluable participants, will be used (limited to those concentration for which the dates, times and dose amounts of DTG in the days leading up to the PK visit are available).

4.2.3 Safety Analysis Population

Safety Analysis Population: The Safety Analysis Population consist of all participants who have taken at least one dose of RPT, at least one dose of INH, and at least 2 doses of DTG (Arm 1) or at least 1 dose of DTG (Arm 2).

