There are less data when DTG is given with RPT as compared to rifampin. In a small study assessing the PK and safety of DTG when given at a dose of 50 mg once-daily together with once-weekly INH and RPT (each dosed at 900 mg, 3HP) in HIV-uninfected healthy volunteers, DTG trough (C_{12}) concentrations were reduced by 43%, 74%, and 53% 2, 3, and 6 days after the dose, respectively, compared to when DTG was given alone [10]. The lowest average C_{12} , though, remained 5.3 times higher than the protein-adjusted IC_{90} for DTG, suggesting that even with these reductions in exposure, virologic suppression was likely to be maintained in individuals with HIV taking standard-dose DTG. The combination, however, was poorly-tolerated, with flu-like syndrome seen in two of three volunteers. Brisk immune responses have been seen in healthy volunteers given rifamycins previously [6, 11-13] and in individuals with TB. Rifamycin hypersensitivity is most common when rifamycins are dosed intermittently [14, 15].

In a similar study of 3HP in HIV/latent TB infection (LTBI) co-infected individuals, Dooley and colleagues conducted PK sampling of patients receiving 50 mg DTG in combination with once weekly RPT and INH. The geometric mean (GM) trough concentration of DTG pre-HP treatment was 1003 ug/mL (5th-95th percentile: 500-2080), and during HP treatment 546 (134-1616) with all trough concentrations except for one above the DTG IC_{90} of 64 ug/mL. Overall, although weekly HP decreased DTG bioavailability, which was associated with a modest decrease in trough concentrations, all trough concentration except for one were above the DTG IC_{90} , and DTG clearance remained unchanged after the 8th weekly dose of RPT/INH. Notably, with regard to safety, co-administration of DTG and weekly HP was well-tolerated, with no HP-related Grade >3 AEs. All viral loads were suppressed [16]. These data, combined with the week 48 results of the INSPIRING study [7] add to the evidence in that safety events such as those seen in the Brooks et al. study [10] present differently in healthy volunteers versus HIV/LTBI co-infected individuals.

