4.0 SELECTION AND ENROLLMENT OF PARTICIPANTS

4.1 Inclusion Criteria

- 4.1.1 Males and females at least 18 but no more than 65 years of age at study entry.
- 4.1.2 Ability and willingness of participant or legal guardian/representative to provide informed consent.
- 4.1.3 Weight \geq 40 kg and a body mass index (BMI) of greater than 18.5 kg/m².
- 4.1.4 Documentation of HIV-1 infection status, as below:

HIV-1 infection, documented by any licensed rapid HIV test or HIV-1 E/CIA test kit at any time prior to entry and confirmed by a licensed Western blot or a second antibody test by a method other than the initial rapid HIV and/or E/CIA, or by HIV-1 antigen or plasma HIV-1 RNA viral load. Two or more HIV-1 RNA viral loads of $>1,000$ copies/mL are also acceptable as documentation of HIV-1 infection.

Note A: The term “licensed” refers to a US FDA-approved kit, which is required for all IND studies, or for sites that are located in countries other than the United States, a kit that has been certified or licensed by an oversight body within that country and validated internally. Non-US sites are encouraged to use US FDA-approved methods for IND studies.

Note B: WHO and Centers for Disease Control and Prevention (CDC) guidelines mandate that confirmation of the initial test result must use a test that is different from the one used for the initial assessment. A reactive initial rapid test should be confirmed by either another type of rapid assay or an E/CIA that is based on

a different antigen preparation and/or different test principle (e.g., indirect versus competitive), or a Western blot or a plasma HIV-1 RNA viral load.

4.1.5 HIV-1 plasma viral load <50 copies/mL obtained within 30 days prior to study entry by any US laboratory that has a Clinical Laboratory Improvement Amendments (CLIA) certification or its equivalent, or at any network-approved non-US laboratory that is Virology Quality Assessment (VQA) certified.

4.1.6 At US sites: Evidence of LTBI by tuberculin skin test (TST) reactivity ≥ 5 mm, or a positive interferon gamma release assay (IGRA) at any time prior to study entry.

At non-US sites: Indication for LTBI treatment according to WHO latent TB guidelines (Note: TST/IGRA results not required).

4.1.7 On a stable once daily DTG (50 mg) based ART with once daily 2 NRTIs and

- With at least 28 total days of DTG and NRTI dosing prior to study entry

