5.1 Regimens and Duration

Arm 1

- DTG 50 mg orally BID (~12 hours apart)
 - 1st dose: DTG 50 mg each morning from non-study ARV supply
 - 2nd dose: DTG 50 mg each evening from study supply
- 1HP: INH 300 mg + RPT 600 mg orally each morning for 4 weeks

Arm 2 (upon opening)

- DTG 50 mg orally each morning from non-study ARV supply
- 1HP: INH 300 mg + RPT 600 mg orally each morning for 4 weeks

All participants must be on stable once-daily DTG-based ART with 2 nucleoside reverse transcriptase inhibitors (NRTI).

All participants must receive pyridoxine (vitamin B6) 25 or 50 mg with each dose of INH based on the current local, national, or international dosing guidelines. Pyridoxine is not provided by the study.

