5.2 Administration and Dispensing

Dolutegravir (DTG) will be administered orally as 50 mg either QD or BID. As RPT and INH will be given with food, the DTG dose when aligned with 1HP administration will be given with food as well. DTG doses not aligned with 1HP doses may be given with or without food with exception of DTG doses taken on Day 0 and Day 28, which should be taken with food. Separate each DTG 50 mg dose by 12 hours when giving BID. In Arm 1, 1HP should be taken with the first daily dose of DTG.

Isoniazid (INH) will be administered orally as 300 mg QD. INH may be taken with food and at the same time as rifapentine. The 300 mg tablets must not be divided or crushed.

Rifapentine (RPT) will be administered orally as 600 mg QD with food.

To align with the PK sample collections, participants should be on morning dosing regimen for the duration of the study (except the 2nd dose DTG in Arm 1), including at least 3 days prior to Day 0 intensive PK. The dose on the morning of PK sampling day will be an observed dose. Thus, participants will need to hold the dose until the clinic visit.

1HP medications will be provided for Day 1 to Day 28. DTG 50 mg tablets will be dispensed to participants in Arm 1 of the study for the second daily dose of DTG. Participants will continue 2 NRTI plus one dose DTG 50 mg daily from their own supply while on the study treatment regimen in both Arm 1 and Arm 2 (Day 1 to Day 28). Participants will have up to 6 weeks from enrollment to complete 4 weeks of 1HP treatment. Following 1HP, participants will continue antiretroviral therapy prescribed by their routine HIV care provider.

The 1HP treatment is ideally taken once daily for 28 consecutive days. If doses are interrupted, participants are allowed up to 42 days to complete the 1HP therapy. For Arm 1 participants, BID dosing of DTG should continue for the entire 1HP treatment, up to 42 days. Additional doses of DTG for Arm 1 may be dispensed as required, either in intact bottles or dispensed into prescription bottles. For Arm 2 participants, daily DTG and NRTIs should continue from their own supply for the entire 1HP treatment.

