6.3.11 Pharmacokinetic Sampling

Intensive PK

A 24 hour intensive PK sampling will occur per the SOE.

Arm 1

The intensive plasma PK samples will be collected at hours 0 (pre-dose), 1, 2, 4, 8, 12, 13, 14, 23, and 24 hours post-DTG dose at Entry/Day 0 and on Day 28 (-2/+14 days).

Arm 2

The intensive plasma PK samples will be collected at hours 0 (pre-dose), 1, 2, 4, 8, 12, 23 and 24 hours post-DTG dose at Entry/Day 0 and on Day 28 (-2/+14 days).

NOTE: For Arms 1 and 2, a minimum of 6 samples must be collected, including the 23- and 24-hour collections.

All intensive samples should be collected within a 15 minutes window of the designated sampling time. The following should be recorded:

- Date and time of sampling
- Time of dosing of three prior days of ART and/or 1HP per participant self report
- Time of dosing of ART and/or 1HP taken during the PK sampling
- Whether DTG, RPT, INH, NRTI doses were taken with food

NOTE: The Entry/Day 0 DTG dose is from participant's existing ART regimen and should be taken with food. Entry/Day 0 PK sampling may only occur after ensuring 3 days of consecutive dosing of ART prior to entry. Day 28 visit may occur up to 2 weeks later as participants will have 6 weeks to complete 4 weeks of on-study treatment. However, PK sampling at Day 28 may only occur after ensuring 3 days of consecutive dosing of ART and RPT/INH prior to study visit. Day 28 DTG dose should be taken with food.

Sparse PK

The sparse plasma PK samples will be collected per the SOE at 20 minutes (± 15 minutes) (trough) before the dose.

All sparse samples should be collected within the designated window above. The following should be recorded:

- Date and time of sampling
- Time of dosing of three prior days of ART and 1HP per participant self report.
Of note, Day 3 sparse PK may have only two prior days of 1HP.
- Time of dosing of ART and 1HP taken during the PK sampling
- Whether DTG, RPT, INH, NRTI doses were taken with food

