2.1 Overview of Study Design

A5372 is an open-label, non-randomized, two-arm, multicenter PK study to investigate the potential interactions between DTG and steady state RPT when RPT is prescribed with INH daily for 4 weeks (1HP) in HIV-1 and LTBI co-infected individuals.

The study regimen will be as follows, days 1 through 28.

Arm 1

- DTG 50 mg orally BID (~12 hours apart)
 - 1st dose: DTG 50 mg each morning from non-study ARV supply
 - 2nd dose: DTG 50 mg each evening from study supply
- 1HP: INH 300 mg + RPT 600 mg orally each morning for 4 weeks

Arm 2 (upon opening; contingent on assessment of DTG PK data from participants in Arm 1)

- DTG 50 mg orally each morning from non-study ARV supply
- 1HP: INH 300 mg + RPT 600 mg orally each morning for 4 weeks

All participants must also be on once-daily DTG-based ARV treatment with 2 NRTIs (excluding TAF) during the study. All participants must receive pyridoxine (vitamin B6) 25 or 50 mg with each dose of INH based on the current local, national, or international dosing guidelines.

Initially, the study will open with Arm 1. Once DTG concentrations data from the first 32 evaluable participants in Arm 1 are available, the core team will review the DTG PK data to ensure sufficient plasma exposures of DTG (C_{tau}) are achieved with twice-daily DTG dosing. This review will consist summarizing data completeness, participant evaluability for PK, and observed minimum concentrations. Provided: (1) there are 32 evaluable participants with minimum concentrations, (2) these minimum concentrations are above 158 ng/mL, and (3) there are no worrisome outliers among these minimum concentrations, the PK data will be used to model the anticipated PK of QD DTG when coadministered with 1HP. Based on these models and simulations of QD DTG dosing with 1HP, a decision will be made on whether to open Arm 2 for enrollment. Details on the criteria for opening Arm 2 are given in the protocol (Section 7.4) and herein (Section 4.5).

Plasma PK profiles for DTG will be determined at two time points. At the first time point, plasma samples will be drawn in participants at steady state with respect to DTG when receiving once daily DTG prior to 1HP. At the second time point, DTG will be given BID in Arm 1 and QD in Arm 2 during the 1HP LTBI regimen; PK sampling for DTG will occur on day 28 of the 1HP regimen.

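### The Arm 1 Safety Analysis Population requires two DTG doses with no counting window, so a participant who stops all DTG after the first morning's dosing can drop out of the pre-specified safety proportions

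*SAP*

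**What the plan says.** SAP 4.2.3 defines the Safety Analysis Population by three conditions that must all be met. For Arm 1 they are "at least one dose of RPT, at least one dose of INH, and at least 2 doses of DTG (Arm 1"). For Arm 2 the RPT and INH conditions are the same but the DTG condition is lower: "or at least 1 dose of DTG (Arm 2"). The section gives no start date for counting doses and does not say whether DTG from the participant's own supply counts.

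The order of dosing on the first day matters here. Protocol 5.2 says "In Arm 1, 1HP should be taken with the first daily dose of DTG". SAP 2.1 describes that dose as "1st dose: DTG 50 mg each morning from non-study ARV supply", and Protocol 5.1 adds "2nd dose: DTG 50 mg each evening from study supply".

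Every participant is already taking DTG. Protocol 4.1 requires "With at least 28 total days of DTG and NRTI dosing prior to study entry", and Protocol 6.3.11 notes that "The Entry/Day 0 DTG dose is from participant's existing ART regimen and should be taken with food".

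SAP 4.9 and 5.9 use this population for AEs, SAEs, discontinuations and HIV-1 RNA above 50 copies/mL. SAP 5.6 and 5.7 use it for pregnancies and deaths.

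**The concern.** A safety set should not depend on what happened after the first exposure. In Arm 1 the two-dose condition can only be met, counting from Day 1, by someone who is still taking DTG on the evening of Day 1 or later. A participant who has an event that morning and stops all DTG fails it because of the outcome the set is meant to measure. The same history in Arm 2 passes.

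The secondary safety and tolerability proportions are among the results meant for the primary manuscript and for registry posting (Protocol 10.2, SAP 1.1). The protocol treats reactions to rifamycins as a live question: it reports a small healthy-volunteer study of DTG with weekly RPT and INH, "with flu-like syndrome seen in two of three volunteers" (Protocol 2.1.1), and gives rifamycin hypersensitivity its own management section (8.2).

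**Working it through.** The plan states no figure for the size of the safety set, so there is nothing to reproduce. The check traces the definition through the dosing schedule and then sizes the effect with the SAP's own interval method.

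**Step 1. Count DTG doses for a participant who takes the Day 1 morning doses, reacts and stops.** RPT and INH are each taken once, so those conditions are met. Only the DTG count varies.

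| Reading and course | Arm 1 DTG doses | Arm 1 (needs 2) | Arm 2 (needs 1) |
|---|---|---|---|
| (a) Count from Day 1; all DTG, own supply included, stops before the evening | 1 | excluded | included |
| (b) Count from Day 1; RPT, INH and study-supplied DTG stop, own morning DTG continues | 1 + 1 = 2 by the Day 2 morning | included | included |
| (c) Count any DTG, including before Day 1 | Day 0 + Day 1 = 2 at least | included | included |

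Reading (c) makes the DTG condition empty, since entry already requires 28 days of DTG. Counting from Day 1 is the only reading on which the condition does anything, and on it case (a) is lost.

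**Step 2. Which outputs lose the participant in case (a).**
- Lost: the proportions in SAP 4.9 and 5.9, and the pregnancy and mortality summaries in 5.6 and 5.7.
- Kept, because no such restriction is stated: the flow diagram (5.1), off-study reasons (5.4), reasons for discontinuing study drug (5.5), expedited reporting (Protocol 7.3) and the halting rule at three participants with related Grade 3 or higher events (Protocol 10.5.1, SAP 2.5).

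**Step 3. Size.** Inputs: 36 enrolled per arm (SAP 2.4); exact 95% Clopper-Pearson intervals (SAP 4.9). For x events in n participants the limits are the 0.025 quantile of Beta(x, n − x + 1) and the 0.975 quantile of Beta(x + 1, n − x). With x = 0 the lower limit is 0 and the upper limit is 1 − 0.025^(1/n); for n = 35 that is 10.0%.

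The number of participants in case (a) is an assumption, shown as a range. With no other events in the arm:

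| Number in case (a) | Counted | Dropped |
|---|---|---|
| 1 | 1/36 = 2.8% (0.1 to 14.5) | 0/35 = 0% (0 to 10.0) |
| 2 | 2/36 = 5.6% (0.7 to 18.7) | 0/34 = 0% (0 to 10.3) |
| 3 | 3/36 = 8.3% (1.8 to 22.5) | 0/33 = 0% (0 to 10.6) |

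With one such participant and two other participants with events, 3/36 = 8.3% (1.8 to 22.5) becomes 2/35 = 5.7% (0.7 to 19.2).

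**Step 4. Direction for HIV-1 RNA.** An excluded participant who stays suppressed leaves only the denominator, so k/36 becomes k/35 and the proportion rises slightly. The downward bias therefore applies to the AE and discontinuation proportions, not to the virologic one.

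**The case against.** A reader might infer that such a participant vanishes from every safety result. The documents do not support that: the outputs listed as kept in Step 2 would still show the person, including a discontinuation attributed to a treatment-related AE, and the person would count toward halting if the event is Grade 3 or higher and judged related. A reader might also infer that the rule can only flatter safety; Step 4 shows that this fails for HIV-1 RNA.

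The losing case is also narrow. For suspected rifamycin hypersensitivity, Protocol 8.2 stops the study-provided drugs and does not require own-supply DTG to stop, so a participant who stays on ART reaches two doses the next morning. Own-supply DTG must stop for Grade 3 or higher allergic reactions considered related to DTG (8.3) and for Grade 3 or 4 suicidal ideation (8.4). Elsewhere in Protocol 8 it depends on the investigator's causality assessment. The protocol gives no onset time for the flu-like syndrome it cites, which arose with weekly dosing in healthy volunteers, and in its study of weekly treatment in people with HIV all 60 who started completed (2.2).

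Finally, two doses BID and one dose QD each make one day of assigned DTG, the arms are sequential and not randomized, and no between-arm safety test is planned.

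These points limit how often the rule bites and where. They do not give a reason for a safety set to require a second dose. The one-day rationale explains the difference between arms, but it still conditions Arm 1 membership on continuing to the evening.

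**Conclusion.** The point holds in a limited form. Read from Day 1, SAP 4.2.3 excludes an Arm 1 participant who stops all DTG before the first evening dose, and so selects on the outcome in the pre-specified AE and discontinuation proportions. Read without a start date, the DTG condition is redundant. Either way the sentence needs changing.

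Each participant lost costs about 2.8 percentage points at n = 36 when there are no other events, and lowers the upper confidence limit (14.5% to 10.0% for one participant). These figures rest on assumed counts; nothing in the documents predicts how many participants would meet the condition, and the number is probably zero or very small. The joint RPT and INH requirement adds little in practice, since both are due the same morning.

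**What to change.** Replace SAP 4.2.3 with a single definition for both arms: all participants who, on or after Day 1, took at least one dose of any study-supplied drug, meaning RPT or INH or, in Arm 1, the study-supplied DTG. Drop the minimum number of DTG doses.

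Tying the rule to study-supplied drugs is deliberate. A broader rule that accepted any DTG from Day 1 would admit Arm 2 participants who never took 1HP and simply continued their usual DTG.

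The cost is one SAP sentence and a version entry, ideally made before the Arm 1 safety outputs are run. Dosing, sampling and sample size do not change. The small downside is that someone who took only part of the combination would be included; a footnote giving the number of such participants would cover it.
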